Official Title: The HistoSonics System for treatment of primary and metastatic liver tumors using

histotripsy (#HOPE4LIVER US)

NCT Number: NCT04572633

Protocol Date: February 15, 2022 (CSP1427 Revision F)

Title	The HistoSonics System for treatment of primary and metastatic liver tumors using histotripsy (#HOPE4LIVER US)
Clinical Investigation Protocol Identification Code	#HOPE4LIVER US Sponsor Clinical Study Number: CSP1427 Revision F (15Feb2022) ClinicalTrials.gov Identifier: NCT04572633
Trial Purpose	The #HOPE4LIVER US clinical trial data will be utilized to gain approval in commercializing the HistoSonics System.
Trial Design	This trial is a single arm, non-randomized prospective trial. Following histotripsy treatment of liver tumor(s), subjects will undergo imaging ≤36 hours post-index procedure to determine technical success. Subjects will then be followed for 30 days. Additionally, subjects will be evaluated at 6 months and followed annually for up to five (5) years post-index procedure.
Trial Population	Subjects who are 18 years of age or older with a diagnosis of primary or metastatic (from other primary cancers) liver cancer.
Objective	The objective of this trial is to evaluate the efficacy and safety of the HistoSonics System for the treatment of primary or metastatic tumors located in the liver.
Device Name	HistoSonics System (System)
IDE Indications for Use	The HistoSonics System is intended for the destruction of liver tissue using histotripsy, a non-thermal, mechanical process using focused ultrasound.
Enrollment	Up to forty-five (45) subjects enrolled targeting forty (40) evaluable subjects at up to eight (8) US clinical sites
Duration of Trial	The duration of this trial is expected to be approximately six and a half (6.5) years.
Primary Endpoints	Co-primary endpoints:
	 Efficacy: Technical success as determined, at ≤36 hours post-index procedure, by evaluating the histotripsy treatment size and coverage. Technical success is defined as the treatment volume/treatment dimensions being greater than or equal to the targeted tumor with complete tumor coverage, via CT or MR imaging. [Core Lab Adjudicated] [≤36 hours post-index procedure]
	2. Safety: Index procedure related major complications, including device-related events, defined as Common Terminology Criteria for Adverse Events (CTCAE) grade 3 or higher toxicities, up to 30 days post index-procedure
	[Clinical Events Committee Adjudicated] [30-Day post-index procedure]

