	The proportion of observed Technical Success by lesion on those with evaluable imaging will be reported. As up to 3 treated lesions are allowed per subject, the 95% confidence interval for the observed Technical Success rate will be estimated by the bootstrap sampling with replacement method to account for potential within-subject lesion correlations. A subject will be the bootstrap sampling unit. A > 70% lower limit for the 95% confidence interval will indicate the HistoSonics Technical Success rate as statistically significantly higher than the performance goal of 70% at a 1-sided p < 0.025 level.
	Primary Safety
	A safety performance goal of 25% was established and the hypothesis was as follows:
	Null hypothesis: HistoSonics major complications patient incidence rate ≥25%
	Alternative hypothesis: HistoSonics major complications patient incidence rate <25%
	The patient incidence rate of index-procedure related major complications and its two-sided 95% Wilson Score CI will be calculated based on all subjects enrolled. The upper limit of the 95% CI must be <25% in order to regard the index procedure's safety as acceptable.

Secondary endpoints will be presented descriptively with no hypothesis test.

Determination of Sample Size

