A 5% - 10% attrition rate was anticipated; reasons for attrition included: both anticipated and unanticipated drop-out (e.g., subject withdrawal, loss-to-follow-up, and death) as well as the inability for the Core Laboratory to assess the primary efficacy endpoint due to missing or non-evaluable imaging. Therefore, up to forty-five (45) subjects were targeted for enrollment; subject replacement was not applicable in these cases.

Primary Analysis

The primary analyses of all primary and secondary endpoints will be performed after forty (40) evaluable subjects have been enrolled between the #HOPE4LIVER US (NCT04572633) and #HOPE4LIVER EU/UK (NCT04573881) trials and after those subjects have finished the 30-day assessment. This analysis will include at a minimum 10 subjects (25%) enrolled in the US. Data will be pooled between the two studies for the purposes of assessing the primary endpoints.

Bibliography

	2. Kim Y sun, Lim HK, Rhim H, et al. Ten-year outcomes of percutaneous radiofrequency ablation as first-line therapy of early hepatocellular carcinoma: analysis of prognostic factors. J Hepatol . 2013;58(1):89-97. doi:10.1016/j.jhep.2012.09.020

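### Minor: the 30-day safety rate is taken over all enrolled subjects, but the analysis waits only for the 40 evaluable ones, so untreated or still-pending subjects can count as non-events

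*Combined protocol and SAP*

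**What the plan says.** All references are to the combined protocol and SAP.

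- **Statistical Methods, Primary Safety.** The major-complication rate and its "two-sided 95% Wilson Score CI will be calculated based on all subjects enrolled". The upper limit must lie below 25%. The endpoint window runs to 30 days after the index procedure (Primary Endpoints), and both co-primary results must be positive.
- **Primary Analysis.** "The primary analyses of all primary and secondary endpoints will be performed after forty (40) evaluable subjects have been enrolled" across the US and EU/UK trials, and "after those subjects have finished the 30-day assessment". Also: "Data will be pooled between the two studies for the purposes of assessing the primary endpoints".
- **Enrollment.** "Up to forty-five (45) subjects enrolled targeting forty (40) evaluable subjects", stated for the US sites.
- **Determination of Sample Size.** "A 5% - 10% attrition rate was anticipated". The reasons include withdrawal, loss to follow-up and death, and also "inability for the Core Laboratory to assess the primary efficacy endpoint due to missing or non-evaluable imaging". Such subjects are not replaced.
- **Trial Design and Follow-Up Visits.** "subjects will undergo imaging ≤36 hours post-index procedure to determine technical success", and visits at day 14 and day 30 are planned for every enrolled subject.

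The text defines neither enrolled nor evaluable. It gives no rule for an enrolled subject whose 30-day safety follow-up is incomplete when the analysis is run.

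**The concern.** The denominator and the trigger refer to different groups. The denominator takes in everyone enrolled, while the trigger requires complete follow-up only from the 40 evaluable subjects. In a plain proportion, an enrolled subject with no recorded event is a non-event, whether or not anyone observed the 30 days. For a complication rate tested against an upper bound, this error runs one way: it makes the device look safer.

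Two kinds of subject have little or no observed risk: those enrolled but never treated, and those treated after the 40th evaluable subject who are not yet at day 30 when the analysis runs. At a borderline count they could turn a fail on the observed subjects into a pass, on one of two results that the trial must win. With no rule in the text, their handling would be chosen after the data are seen.

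**Working it through.** **Inputs.** Goal 25%, two-sided 95% Wilson interval, all-enrolled denominator (Primary Safety). Design case 4/40 and true rate 7% (Determination of Sample Size). 40 evaluable subjects (Primary Analysis). Attrition 5% to 10%.

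**Formula.** With p = x/n and z = 1.96, the Wilson upper limit is

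U = [p + z²/(2n) + z√(p(1−p)/n + z²/(4n²))] / (1 + z²/n).

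**The plan's own figures.** 4/40 gives 3.96% to 23.05%, which matches the stated 4.0% to 23.1%. P(X ≤ 4 | n = 40, 7%) = 0.855, which matches the stated power of about 0.85.

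**Enrolled total (assumption).** The pooled total is not stated. 40/0.95 = 42.1 and 40/0.90 = 44.4, which round up to 43 and 45. I use 43 to 45.

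**Upper limit by denominator.** For 5/42: (0.11905 + 0.04573 + 0.10809)/1.09146 = 0.250004.

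| n | U at 5 events | Below 25%? |
|---|---|---|
| 40 | 26.11% | no |
| 41 | 25.54% | no |
| 42 | 25.0004% | no |
| 43 | 24.48% | yes |
| 44 | 23.98% | yes |
| 45 | 23.50% | yes |

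The largest passing count is 4 for n = 37 to 42 and 5 for n = 43 to 47. At 5 events, removing 1 unobserved subject of 43, 2 of 44 or 3 of 45 brings n to 42 and turns the pass into a fail. At 4 or fewer events, removing them changes nothing for n between 40 and 45.

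**Outside that range.** The step recurs at larger totals: 6 events give 25.17% at 47 and 24.70% at 48. If unobserved subjects are counted as events instead of being removed, a pass at 4 events can also be overturned: 4/41 gives 22.55%, but with one unobserved subject counted as an event, 5/41 gives 25.54%.

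**False-pass probability at a true 25%, pass limit 5.** Let m of N subjects be incompletely observed, with a fraction f of their 30-day risk observed (f is an assumption):

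P = Σₖ Bin(k; m, 0.25f) · P(X ≤ 5−k | N−m, 0.25).

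| N | m | f = 0 | f = 0.5 | f = 0.75 | complete |
|---|---|---|---|---|---|
| 43 | 1 | 0.0307 | 0.0282 | 0.0269 | 0.0257 |
| 44 | 2 | 0.0307 | 0.0259 | 0.0236 | 0.0215 |
| 45 | 3 | 0.0307 | 0.0238 | 0.0207 | 0.0179 |
| 45 | 4 | 0.0365 | 0.0261 | 0.0217 | 0.0179 |

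The nominal level is 0.025.

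**Chance of the borderline count.** At the plan's 7% rate and complete follow-up, exactly 5 events has probability 0.103, 0.108 and 0.113 at 43, 44 and 45 enrolled. The verdict changes only if enough subjects are also unobserved.

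**The case against.** An all-enrolled safety denominator is an ordinary choice, and it keeps events recorded in subjects who later drop out. The Follow-Up Visits row gives every enrolled subject post-procedure visits, which suggests that enrolled means treated. A treated subject has imaging within 36 hours and a visit at day 14, so some of the risk is observed before any drop-out. If evaluability rests on the early imaging, anyone treated before the 40th evaluable subject has passed day 30 when that subject does, so only later-treated subjects can be pending. Part of the attrition is imaging failure, and those subjects may have complete safety data. The fail at 42 is by 0.0004 percentage points. All of this stands, and it is why the point is minor.

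Three stronger readings are tempting but not supported:

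- *The safety test has an inflated error rate.* If only 40 of 43 to 45 subjects were observed and the rest not at all, the false-pass probability would be P(X ≤ 5 | n = 40, 25%) = 0.043. The documents do not imply that every non-evaluable subject is wholly unobserved. For partly observed drop-outs the rate stays near nominal, and the Wilson rule already gives 0.0257 at 43 with complete follow-up.
- *Treated drop-outs should be removed from the primary test.* Removing early exits without an event while keeping early exits with one makes exclusion depend on outcome and biases the rate upward. Disagreement with such an analysis is not clean evidence of a false pass.
- *The problem exists only at 43 to 45 enrolled, and nothing changes at 40 to 42.* That rests on an assumed pooled total and on the removal comparison alone; the 6-event step and the 5/41 case show otherwise.

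What the objection does not answer is that enrolled is undefined and that no sentence makes the analysis wait for everyone in the denominator.

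**Conclusion.** The gap is real and minor. Followed literally, the plan can count untreated or still-pending subjects as non-events in a test that the trial must win, and the bias goes only in the device's favour. With 43 to 45 enrolled, removing those subjects changes the decision only at 5 events. A false-pass probability of 0.031 to 0.037 needs wholly unobserved subjects, which fits untreated or just-enrolled ones. For treated drop-outs with half to three quarters of their risk observed it is about 0.021 to 0.028, against 0.018 to 0.026 with complete follow-up. These figures rest on the assumed pooled total, the assumed fractions observed, and the reading that a subject with no recorded event counts as event-free. They concern the safety endpoint alone; trial success also needs the efficacy result.

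**What to change.** 1. Define the primary safety set as all subjects in whom the index procedure was started, whether or not their imaging is evaluable. List enrolled-but-untreated subjects separately.
2. Run the primary safety analysis only when every subject in that set has reached day 30 or exited.
3. Keep the Wilson test as the deciding analysis. State that a treated subject who exits before day 30 with no recorded event counts as a non-event in it. Report how many such subjects there are and the last day each was observed.
4. Add one sensitivity analysis that does not decide the trial: either a 30-day rate that uses observed follow-up time (for example Kaplan-Meier) or a tipping-point analysis over the early exits. Do not use an analysis that simply drops them.

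The cost is a few sentences and one table, with no extra subjects and no change of test or performance goal. The downside is a wait of at most 30 days for subjects already treated, and a possibly slightly less favourable rate.

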A literature review was conducted to identify rates of technical success in published studies on microwave and radiofrequency ablation of primary and metastatic liver tumors from 2010 to 2020. Eight studies reporting on 2,876 total tumors were assessed with a mean, weighted mean, and median rate of 81.5%, 86.6%, and 92.0%, respectively^{1–8}. Sample size was determined from primary efficacy of technical success assuming one treated lesion per subject for simplicity. Forty evaluable subjects were targeted for enrollment. Using a technical success acceptance level of 85% (34/40 lesions), which is consistent with the literature review results, the Wilson Score 95% confidence interval is 70.9% to 92.9%. Using the lower limit of the 95% confidence interval, a null hypothesis of ≤70% success rate can be rejected at a 1-sided p<0.025 significance level. By binomial probability calculation, the false positive (alpha) error for this design is 0.024. Assuming a true histotripsy technical success rate of 90%, the power for observing ≥34/40=85% in the trial is approximately 0.90. Due to the allowance of up to three (3) treated lesions per subject, the actual 95% confidence interval for the lesion based technical success rate would be estimated by the bootstrap sampling with replacement method and subject would be the sampling unit. The confidence interval would be narrower, and the power would be higher than the above estimates.

A similar review of major complications (CTCAE grade 3 or higher equivalent) when treating liver lesions with radiofrequency ablation identified 5 independent studies reporting on 1,935 patients and one review article encompassing 32 studies^{1–5,9}. Major complication rates ranged from 2.0% to 11.2%. For a new technology such as histotripsy, a conservative assumption for major complications was assumed to be close to the upper end of the literature results of 11.2%. Accordingly, with the sample size of 40 participants and a histotripsy major complication rate of 10% (4/40 participants), the Wilson Score 95% confidence interval is 4.0% to 23.1%. Assuming a true histotripsy event rate of 7%, the power of observing <4/40=10% in the trial is approximately 0.85.

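### Is the safety power of about 0.85 overstated because it is printed for strictly fewer than 4 events in 40?

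*Combined protocol and SAP*

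**What the plan says.** Three places bear on this.

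- **Determination of Sample Size, safety paragraph.** The plan takes 4 events in 40 as its reference result: for "a histotripsy major complication rate of 10% (4/40 participants), the Wilson Score 95% confidence interval is 4.0% to 23.1" percent. The next sentence gives the power: "Assuming a true histotripsy event rate of 7%, the power of observing <4/40=10% in the trial is approximately 0.85".
- **Statistical Methods, Primary Safety.** The success criterion uses the two-sided 95% Wilson interval for the patient incidence of major complications among all enrolled subjects: "The upper limit of the 95% CI must be <25" percent. No other criterion for safety success is given.
- **Determination of Sample Size, efficacy paragraph.** The sample size comes from technical success. The power statement there uses an inclusive sign: "the power for observing ≥34/40=85% in the trial is approximately 0.90". The type I error is given as well: "By binomial probability calculation, the false positive (alpha) error for this design is 0.024".

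**The concern.** In a power statement the inequality defines the event whose probability is reported. Here the printed event excludes exactly 4 of 40, yet the figure beside it is too large for that event. Anyone who recomputes it gets 0.69.

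Safety is a co-primary endpoint, both endpoints must be positive for the trial to succeed, and the data are meant to support marketing approval. If the 0.85 were wrong, the safety endpoint would have materially less power at 7% than stated. If instead the sign were meant as printed, the sample size section would imply a limit of 3 events while the Primary Safety criterion allows 4, and the two would conflict on a result of exactly 4/40. Either reading would deserve a correction.

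**Working it through.** **Inputs.** From Determination of Sample Size: n = 40, true rate 7%, reference count 4, stated power about 0.85; for efficacy, cut-off 34/40, rates 70% and 90%, stated type I error 0.024 and power 0.90. From Primary Safety: performance goal 25%, two-sided 95% Wilson interval.

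**1. Reproduce the stated power.** Let X be Binomial(40, 0.07), with P(X = k) = C(40, k) × 0.07^k × 0.93^(40−k).

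- P(X ≤ 2) = 0.4625 and P(X = 3) = 0.2312, so P(X < 4) = P(X ≤ 3) = 0.6937.
- P(X = 4) = 0.1609, so P(X ≤ 4) = 0.6937 + 0.1609 = 0.8546.

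The stated 0.85 is the inclusive probability. Approximations do not rescue the strict version: Poisson gives 0.692, the normal with continuity correction 0.668, and the normal without it 0.771. For fewer than 4 events to have probability 0.85, the true rate would have to be about 5.2%.

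**2. Find the count that the success criterion implies.** The Wilson upper limit is [p + z²/(2n) + z√(p(1−p)/n + z²/(4n²))] / (1 + z²/n), with z = 1.96. At n = 40, z²/(2n) = 0.0480, z²/(4n²) = 0.00060 and 1 + z²/n = 1.0960.

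- 4/40: [0.1480 + 1.96 × √(0.00225 + 0.00060)] / 1.0960 = 0.2527 / 1.0960 = 0.2305. This is the plan's own 23.1%, and it passes.
- 5/40: [0.1730 + 1.96 × √(0.00273 + 0.00060)] / 1.0960 = 0.2862 / 1.0960 = 0.2611. It fails.

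The criterion at 40 subjects is therefore X ≤ 4. Its exact type I error at a true rate of 25% is P(X ≤ 4) = 0.016, and its power at 7% is 0.855.

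**3. Compare with the efficacy figures.**

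| Efficacy event, n = 40 | Probability at 70% | Probability at 90% |
|---|---|---|
| At least 34 (inclusive) | 0.0238 | 0.9005 |
| More than 34 (strict) | 0.0086 | 0.794 |
| Stated in the plan | 0.024 | 0.90 |

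The plan's efficacy calculations count the threshold value as a success. The safety calculation did the same, and only its printed sign differs.

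**4. See what depends on the sign.** The Primary Safety criterion is written as a confidence limit and cites no event count. The sample size was fixed from efficacy. No other statement takes the safety count as an input.

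**The case for a change.** The case for a correction is that the sentence is wrong as printed, by an amount that the word approximately cannot cover. It is the only power figure for a co-primary endpoint in a file meant for regulators, and one character would put it right at no cost. A reader who checks it in isolation could think the endpoint underpowered, or infer a limit of 3 events.

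The arithmetic in that case stands. The harm does not. To be misled, a reader would have to overlook the sentence immediately before, where 4/40 has an upper limit of 23.1%, and the criterion that needs only a limit below 25%. It is also uncertain that the sponsor's own file carries the wrong sign. Inclusive signs survive elsewhere in the same section, which argues against a loss in reading the PDF. But an inclusive sign typed as an underlined strict one could lose its underline while true inclusive characters survived. The match between 0.85 and the inclusive event fits either explanation.

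One caution also stands. The figure describes 40 subjects, whereas safety is analysed on all enrolled, and enrolment may reach 45. Under the Wilson criterion, 4 events are allowed at 41 or 42 subjects, with power at 7% of about 0.83 to 0.84. At 43 to 45 subjects 5 are allowed, with power of about 0.91 to 0.92. None of these falls near 0.69, and the plan says openly that its figure is for 40.

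**Conclusion.** This is a clerical slip, and no change to the plan follows. As printed, the event has probability 0.694, and the 0.161 gap to 0.855 is the probability of exactly 4 events. The stated 0.85 is the power the design has at 40 subjects under its only safety criterion. The endpoint is not underpowered relative to what the plan claims at 7%, and no competing limit of 3 events exists, because success is judged by the Wilson upper limit and not by the sample size paragraph. Correcting the sign would be harmless if the text were reissued for another reason, but nothing in the conduct, analysis or conclusion of the trial would differ.

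This rests on independent events with a common rate, 40 subjects in the safety analysis, and the Wilson interval without continuity correction, which reproduces the plan's 4.0% to 23.1%.
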